9.1 Birth Control, Pregnancy and Paternity

Pembrolizumab and/or tavo-EP EP may have adverse effects on a fetus in utero. Furthermore, it is not known if pembrolizumab and/or tavo-EP EP has transient adverse effects on the composition of sperm. Non-pregnant, non-breast-feeding women may be enrolled if they are willing to use 2 methods of birth control or are considered highly unlikely to conceive. Highly unlikely to conceive is defined as 1) surgically sterilized, or 2) postmenopausal (a woman who is ≥ 45 years of age and has not had menses for greater than 1 year will be considered postmenopausal), or 3) not heterosexually active for the duration of the study. The two birth control methods can be either two barrier methods or a barrier method plus a hormonal method to prevent pregnancy. Subjects should start using birth control from study Visit 1 throughout the study period up to 120 days after the last dose of study therapy.

The following are considered adequate barrier methods of contraception: diaphragm, condom (by the partner), copper intrauterine device, sponge, or spermicide. Appropriate hormonal contraceptives will include any registered and marketed contraceptive agent that contains an estrogen and/or a progestational agent (including oral, subcutaneous, intrauterine, or intramuscular agents).

Subjects should be informed that taking the study medication may involve unknown risks to the fetus (unborn baby) if pregnancy were to occur during the study. In order to participate in the study they must adhere to the contraception requirement (described above) for the duration of the study and during the follow-up period defined above. Reporting of Pregnancy and Lactation to the DSMC is required. If there is any question that a subject will not reliably comply with the requirements for contraception, that subject should not be entered into the study.

9.2 Use in Pregnancy

If a subject inadvertently becomes pregnant while on treatment, the subject will immediately be removed from the study. The site will contact the subject at least monthly and document the subject's status until the pregnancy has been completed or terminated. The outcome of the pregnancy will be reported to the UCSF Data Safety Monitoring Committee (DSMC) without delay and within 24 hours if the outcome is a serious adverse experience (e.g., death, abortion, congenital anomaly, or other disabling or life-threatening complication to the mother or newborn). The study investigator will make every effort to obtain permission to follow the outcome of the pregnancy and report the condition of the fetus or newborn to the DSMC. If a male subject impregnates his female partner the study personnel at the site must be informed immediately and the pregnancy reported to the DSMC and followed as described above.

Please note, the investigator will notify Incyte within 24 hours of investigator awareness.

9.3 Use in Nursing Women

It is unknown whether the study agents are excreted in human milk. Since many drugs are excreted in human milk, and because of the potential for serious adverse reactions in the nursing infant, subjects who are breast-feeding are not eligible for enrollment.

10 Correlative Studies

Tumor Biopsy:

The clinical investigator and study pathologist have the responsibility for submitting representative diagnostic material for banking. Please refer to the OncoSec Laboratory manual for detailed instructions regarding these assessments. Patients will have a research biopsy taken from at least one tumor site prior to the initiation of treatment. An additional biopsy should be taken on cycle 2 day 1(+/- 3 days) at progression/end of treatment, and additional biopsies may be performed if clinically indicated.

Biopsy Types

Punch, core, incisional, and excisional biopsy specimens are permitted and should be obtained using standard institutional practices. Tumor biopsy may be formalin fixed and paraffin-embedded or frozen at -80C. If core biopsies are used, 3-4 cores should be taken as feasible, but any attempt to acquire at least one specimen will meet protocol requirements. Fine needle aspiration biopsies are not acceptable. Biopsy requirements may be waived by the PI if biopsies pose an excess risk to the patient.

Blood Immune Response Collection:

Patients will have blood drawn for research as outlined in the *Study Calendar*. Blood for Immune response monitoring will be collected as follow: 40 ml of blood. Specimen distribution and required tubes will be specified in the laboratory manual.

Correlative Analyses:

Correlative analyses include but are not limited to:

- Analysis of paired biopsy specimens for changes in inflammatory gene expression (Nanostring), relative proportion of effector versus regulatory T cells (mIHC), evaluation of elaboration of inflammatory cytokines, T-cell repertoires, clonality, and other hallmarks of immune activation.
- Analysis of circulating T-cell populations for changes in the frequency and effector function of immune cells including short-lived effector cells and memory T cells.
- Analysis of pre- and post-treatment cytokine expression, T-cell repertoire, clonality
- Analysis of functional immune responses using Elispot and other assays.
- Additional assessments that could assist in the understanding of the immune response to cancer at the discretion of the principal investigator

10.1 Future Biomedical Research

Future Biomedical Research on blood and leftover tumor biopsy specimens will be performed on collected samples during this clinical trial. This research may include genetic analyses (DNA), gene expression profiling (RNA), proteomics, metabolomics (serum, plasma) and/or

the measurement of other analytes. This research is for biomarker testing to address emergent questions not described elsewhere in the protocol (as part of the main biomarker correlative objectives). The objective is to explore and identify biomarkers that inform scientific understanding of this therapeutic treatment and tumor biology responses to combination therapy. Such studies will be conducted with appropriate statistical considerations and evaluation of results.

11 Reporting and Documentation of Results

11.1 Evaluation of Efficacy (or Activity)

11.1.1 Antitumor Effect – Solid Tumors

Response and progression in this study will be evaluated using the new international criteria proposed by the Response Evaluation Criteria in Solid Tumors ([RECIST](#)) Committee [JNCI 92(3):205-216, 2000]. Changes in only the largest diameter (unidimensional measurement) of the tumor lesions are used in the RECIST v1.1 criteria.

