3.3.1 Inclusion Criteria

Patient Characteristics

1. Age \geq 18 years old;
2. ECOG performance status 0-2;
3. Life expectancy of at least 4 months;

Disease Characteristics

4. Patients must have histological or cytological diagnosis of carcinoma of the head and neck that is not amenable to surgical resection or locoregional radiation therapy with curative intent;
5. At least one accessible lesion (AL) for intratumoral injection. An AL is defined as meeting the following criteria; (1) at least 0.3 cm x 0.3 cm in longest perpendicular diameters (2) in a suitable location for application of electroporation. Tumors invading the carotid artery or at other sites that the investigator believes to be at high risk of life-threatening hemorrhage should not be injected and these lesions may not be used to meet the inclusion criterion for injectable lesions
6. Measureable disease as defined by RECIST v1.1; at least one lesion where the longest perpendicular diameter is at least 1.0 cm by clinical measurement; or at least 1.0 cm by radiographic imaging for non-nodal lesions; at least 1.5 cm in short axis by radiographic imaging for malignant lymph nodes; If the biopsied lesions were previously irradiated, they must demonstrate either radiographic or pathological evidence of recurrent or residual disease. It is not necessary that this lesion is also an AL.
7. If patient has known brain metastases, they must have stable neurologic status following local therapy (surgery or radiation) for at least 4 weeks without the use of steroids or on stable or decreasing dose of ≤ 10 mg daily prednisone (or equivalent), and must be without neurologic dysfunction that would confound the evaluation of neurologic and other AEs (patients with a history of carcinomatous meningitis are not eligible);

Treatment History

8. Patients may have had prior chemotherapy or immunotherapy or radiation therapy. Any drug related adverse events identified during prior therapy must be well controlled (typically resolution to \leq grade 1, OR resolved upon investigator review prior to initiation of this therapy);
9. No systemic antineoplastic therapy may be received by the patient between the time of the biopsy and the first administration of study treatment;

Consent for Biopsies

10. Patient must agree to any protocol mandated biopsies of tumor (deemed accessible and safe for biopsy by the investigator's assessment) and they must allow acquired tissue to be used for biomarker analysis.

Fertility

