6.1 Efficacy Assessments

Response to treatment in this study will be evaluated using the international criteria proposed by the RECIST Committee (Therasse et al. 2000a), modified in 2009 (Eisenhauer et al. 2009) and clarified for disease-specific adaptation (Schwartz et al. 2016). The primary efficacy endpoint, BORR, will be evaluated using RECIST v1.1 (**Section 6.1.1.1**).

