Complete Response (CR)²	Disappearance of all target lesions, determined by two separate observations conducted not less than 4 weeks apart. Any pathological lymph nodes (whether target or non-target) must have reduction in short axis to <10 mm (the sum may not be "0" if there are target nodes). There can be no appearance of new lesions.	Disappearance of all non-target lesions and normalization of tumor marker level. All lymph nodes must be non-pathological in size (<10 mm short axis).
Partial Response	At least a 30% decrease in the sum of the longest diameter (LD) of target lesions, taking as reference the baseline sum LD. There can be no appearance of new lesions.	Non-target lesions must be non-PD.
Stable Disease (SD)	Neither sufficient shrinkage to qualify for PR nor sufficient increase to qualify for PD, taking as reference the smallest sum LD since the treatment started.	Persistence of one or more non-target lesion(s) and/or maintenance of tumor marker level above the normal limits.

² Patients will meet the primary endpoint (BORR) if they attain a confirmed CR or PR over the 24 weeks with the combination treatment with a 4-week confirmatory scan per RECIST v1.1.

Progressive Disease (PD)	At least a 20% increase in the sum of diameters of measured lesions taking as references the smallest sum of diameters recorded on study (including baseline) AND an absolute increase of ≥ 5 mm, or the appearance of one or more new lesions.	Appearance of one or more new lesions and/or unequivocal progression of existing non-target lesions.
---------------------------------	--	--

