11.1.1.2 Disease Parameters

Measurable disease

Measurable disease is defined as lesions (or tumors) that can be accurately measured in at least one dimension (longest diameter to be recorded) with a minimum size of 10mm by CT scan (irrespective of scanner type), 10mm caliper measurement by clinical exam (when superficial), and/or 20mm by chest X-ray (if clearly defined and surrounded by aerated lung).

All tumor measurements will be recorded in millimeters or decimal fractions of centimeters. Previously irradiated lesions are considered non-measurable except in cases of documented progression of the lesion since the completion of radiation therapy. It is recommended that previously irradiated lesions that would otherwise be considered measurable be followed closely by investigators by comments, measurements and photographs if applicable for retrospective review.

Target lesions

All measurable lesions up to a maximum of 5 lesions total (and a maximum of two lesions per organ) representative of all involved organs should be identified as target lesions and recorded and measured at baseline. Target lesions will be selected on the basis of their size (lesions with the longest diameter) and their suitability for accurate repeated measurements (either by imaging techniques or clinically). A sum of the longest diameter (LD) for all target lesions will

be calculated and reported as the baseline sum LD. The baseline sum LD will be used as reference by which to characterize the objective tumor response.

Non-target lesions

All other lesions (or sites of disease) including any measurable lesions over and above the 5 target lesions should be identified as non-target lesions and should also be recorded at baseline. It is possible to record multiple non-target lesions involving the same organ as a single item on the case record form (e.g. "multiple enlarged pelvic lymph nodes" or "multiple liver metastases"). Bone lesions may be measurable if ≥ 1 cm on MRI. Measurements of these lesions are not required, but the presence or absence of each will be noted throughout follow-up. It is recommended that bone lesions be followed closely by investigators with comments and measurements whenever possible for retrospective review.

Non-measurable disease

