Non-measurable disease is all other lesions (or sites of disease), including small lesions (longest diameter < 20 mm with conventional techniques or < 10 mm using spiral CT scan). Leptomeningeal disease, ascites, pleural or pericardial effusion, inflammatory breast disease, lymphangitic involvement of skin or lung, abdominal masses/abdominal organomegaly identified by physical exam that is not measurable by reproducible imaging techniques are all non-measurable.

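### Nodes qualify and reach CR on short axis, but Sections 6 and 11 both score PR and SD on longest diameter under a RECIST v1.1 endpoint, and Section 11 also carries two conflicting size limits

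*Combined protocol and SAP*

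**What the plan says.** Section 6.1 fixes the criteria for the primary endpoint: "The primary efficacy endpoint, BORR, will be evaluated using RECIST v1.1".

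Two rules measure nodes by short axis:
- Section 3.3.1, criterion 6 (repeated in the synopsis), which presents itself as the RECIST v1.1 definition of measurable disease, requires "at least 1.5 cm in short axis by radiographic imaging for malignant lymph nodes".
- For CR, Table 6-1 says that pathological nodes "must have reduction in short axis to <10 mm", and Section 11.1.1.4 repeats this.

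The remaining scoring rules use longest diameter without separating nodes from other lesions:
- Section 11.1.1.2 defines the baseline reference as "A sum of the longest diameter (LD) for all target lesions".
- Table 6-1 and Section 11.1.1.4 both define PR as a fall of at least 30% in that sum, and both define SD against the smallest such sum.
- Section 11.1.1 presents this as what v1.1 requires, "Changes in only the largest diameter (unidimensional measurement) of the tumor lesions are used in the RECIST v1.1 criteria", while its citation is to the 2000 publication.

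On lesion size, Section 11.1.1.2 defines measurable lesions "with a minimum size of 10mm by CT scan (irrespective of scanner type"). The same section then counts as non-measurable those lesions with "longest diameter < 20 mm with conventional techniques or < 10 mm using spiral CT scan".

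**The concern.** The plan names one set of criteria for its primary endpoint and describes that set in two incompatible ways. Criterion 6 says that under v1.1 a node is measured by short axis. Section 11.1.1 says that v1.1 uses only the largest diameter. A reader who follows the v1.1 label, as criterion 6 describes it, and a reader who follows the written PR rule can therefore classify the same nodal response differently.

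Nodes are not a marginal case here. Section 4.6.1.3 lists palpable lymph nodes among the sites to be injected, and Section 6.1.1 allows a target lesion to be treated or untreated. Scans are read both centrally and by investigators (Section 6.1.1), so two readers working from different parts of the document is a realistic prospect.

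The Stage 1 rule in Section 7.1 turns on 3 responses in 15 patients. One reclassified patient is 1/15 = 6.7 percentage points and can decide whether an arm continues. The comparison is with a historical 15%, so no concurrent control would absorb a change in how responses are scored.

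**Working it through.** **1. The rules for a target node, side by side**

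| Step | Where | Axis and limit |
|---|---|---|
| Measurable at entry | Section 3.3.1, criterion 6 | short axis, 15 mm |
| Measurable, and so available as target | Section 11.1.1.2 | longest diameter, 10 mm by CT; no nodal threshold |
| Baseline sum | Section 11.1.1.2 | longest diameter |
| PR and SD | Table 6-1 and Section 11.1.1.4 | longest diameter |
| PD | Table 6-1 | sum of diameters, axis not stated |
| PD | Section 11.1.1.4 | written as SLD, not defined there |
| CR | Table 6-1 and Section 11.1.1.4 | short axis, below 10 mm |

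The written PR and SD rules agree between Sections 6 and 11. The mismatch is inside each section, between PR/SD and CR, and between both sections and criterion 6.

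**2. Can the axis change a response?** Node sizes below are assumed; the documents give none. Each case is a patient with one target node, no new lesions and no non-target progression. Change = follow-up / baseline - 1, with PR at -30% or lower.

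| Node, mm | Longest diameter | Short axis |
|---|---|---|
| 30 x 20 to 22 x 13 | 22/30 - 1 = -26.7%, SD | 13/20 - 1 = -35.0%, PR |
| 30 x 18 to 24 x 12 | 24/30 - 1 = -20.0%, SD | 12/18 - 1 = -33.3%, PR |
| 30 x 18 to 20 x 14 | 20/30 - 1 = -33.3%, PR | 14/18 - 1 = -22.2%, SD |

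The axis can turn SD into PR or PR into SD. All three nodes meet the 15 mm entry threshold, and none falls below 10 mm.

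The mixed axes also break the ordering of CR and PR. Suppose the second node's short axis fell below 10 mm while its longest diameter stayed at 24 mm. It would meet the nodal condition for CR with a longest-diameter fall of 20%, short of the 30% needed for PR.

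**3. Measurability**
- A node of 20 x 12 mm is measurable under Section 11.1.1.2 (20 mm exceeds 10 mm) but not under criterion 6 (12 mm is below 15 mm).
- A 12 mm non-nodal lesion on non-spiral CT is measurable under criterion 6 (1.0 cm by imaging, no technique condition) and under the definition of measurable disease in Section 11.1.1.2. It is non-measurable under that section's 20 mm limit.
- For spiral CT, both parts of Section 11.1.1.2 give 10 mm, so there is no conflict.

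**4. The design the responses feed.** Section 7.1 gives n1 = 15, n = 28 per arm, continuation at 3 or more, p0 = 15%, p1 = 35%, type I error 0.05 and power 80%. The final cut-off is not stated. I assume success at 8 or more of 28, the lowest value that keeps the error at or below 0.05. Then

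P(success | p) = sum over x = 3 to 15 of P(X1 = x; 15, p) x P(X2 >= 8 - x; 13, p).

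This gives 0.046 at p = 0.15 and 0.803 at p = 0.35, so the stated error and power are reproduced.

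Sensitivity to an assumed shift in the scored response rate:

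| Shift | Error, p0 raised | Power, p1 lowered |
|---|---|---|
| 2 points | 0.085 | 73.7% |
| 5 points | 0.174 | 61.8% |

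These show how sensitive the design is. They do not estimate the shift that the wording would cause.

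**The case against.** The strongest reply is that no two written PR rules clash. A reader might infer that the number of PRs depends on whether Section 6 or Section 11 is applied. The documents do not support that: both state the same 30% fall in the longest-diameter sum, and under either the 30 x 20 mm node is SD. Nor does any section say that nodes enter the sum by short axis. The remark that the sum need not be zero when target nodes are present shows that nodes stay in the sum, but does not name the axis. This stands, and it means the short-axis column above rests on the v1.1 label and on the axis the plan itself uses for nodes at entry and at CR.

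A reader might also take the 20 mm limit to exclude small skin lesions measured by calipers. Section 11.1.1.2 expressly sets 10 mm for calipers, and its non-measurable class is residual, so a lesion already measurable does not fall into it. The term conventional techniques is not defined. Its nearest use is the CT heading in Section 11.1.1.3, where spiral CT is treated separately. The clear conflict is therefore non-spiral CT, and no section says that non-spiral CT will be used.

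Finally, Section 6.1 cites the 2009 revision, and central review covers the first 24 weeks. That lowers the chance of site readers scoring from Section 11 alone. It does not tell the central reader which axis to sum for nodes.

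**Conclusion.** Wrong as written. The scoring rule for the primary endpoint does not match the criteria it names: nodes are judged by short axis at entry and for CR and by longest diameter for PR and SD, in both Sections 6 and 11, and Section 11.1.1 attributes the longest-diameter rule to v1.1 against criterion 6. For a patient whose target disease is nodal, this can move the response between SD and PR (-27% against -35% in the first example).

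The size across the trial cannot be stated. The node sizes are assumed, the documents do not say how many patients have nodal target lesions, and the examples go in both directions. A reader might infer an inflated or deflated BORR; neither is shown.

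The 10 mm and 20 mm limits in Section 11.1.1.2 contradict each other, mainly for non-spiral CT. The consequence is which lesions become targets. A reader might infer that the BORR denominator moves too, since Section 11.1.1.1 ties response evaluability to measurable disease. But Sections 7.2 and 7.3 calculate BORR on All Treated Subjects, and entry is governed by criterion 6, so it does not.

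**What to change.** 1. Keep one response-criteria section, with one RECIST version and one citation, and have the other section refer to it.
2. In Table 6-1 and Sections 11.1.1.2 and 11.1.1.4, define the target-lesion sum as longest diameter for non-nodal lesions and short axis for nodes, in line with the axis already used for nodes at entry and CR. Use that same sum for PR, SD and PD.
3. Correct the sentence in Section 11.1.1 that says v1.1 uses only the largest diameter, and its reference to the 2000 criteria.
4. Carry the 15 mm short-axis nodal threshold of criterion 6 into the definition of measurable disease in Section 11.1.1.2.
5. Delete the 20 mm conventional-technique limit from the non-measurable paragraph, so that it agrees with the 10 mm rule above it and with criterion 6. The chest X-ray limit is separate and is not in conflict.

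The cost is wording only, best settled before scans are read. The sample size and the Stage 1 rule do not change.

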11.1.1.1 Definitions

Evaluable for toxicity

All patients will be evaluable for toxicity from the time of their first treatment with epacadostat, pembrolizumab, or tavo-EP.

Evaluable for objective response

Only those patients who have measurable disease present at baseline, have received at least one cycle of therapy, and have had their disease re-evaluated will be considered evaluable for response. These patients will have their response classified according to the definitions stated below. (Note: Patients who exhibit objective disease progression prior to the end of Cycle 1 will also be considered evaluable).

11.1.1.2 Disease Parameters

Measurable disease

Measurable disease is defined as lesions (or tumors) that can be accurately measured in at least one dimension (longest diameter to be recorded) with a minimum size of 10mm by CT scan (irrespective of scanner type), 10mm caliper measurement by clinical exam (when superficial), and/or 20mm by chest X-ray (if clearly defined and surrounded by aerated lung).

All tumor measurements will be recorded in millimeters or decimal fractions of centimeters. Previously irradiated lesions are considered non-measurable except in cases of documented progression of the lesion since the completion of radiation therapy. It is recommended that previously irradiated lesions that would otherwise be considered measurable be followed closely by investigators by comments, measurements and photographs if applicable for retrospective review.

Target lesions

All measurable lesions up to a maximum of 5 lesions total (and a maximum of two lesions per organ) representative of all involved organs should be identified as target lesions and recorded and measured at baseline. Target lesions will be selected on the basis of their size (lesions with the longest diameter) and their suitability for accurate repeated measurements (either by imaging techniques or clinically). A sum of the longest diameter (LD) for all target lesions will

be calculated and reported as the baseline sum LD. The baseline sum LD will be used as reference by which to characterize the objective tumor response.

Non-target lesions

All other lesions (or sites of disease) including any measurable lesions over and above the 5 target lesions should be identified as non-target lesions and should also be recorded at baseline. It is possible to record multiple non-target lesions involving the same organ as a single item on the case record form (e.g. "multiple enlarged pelvic lymph nodes" or "multiple liver metastases"). Bone lesions may be measurable if ≥ 1 cm on MRI. Measurements of these lesions are not required, but the presence or absence of each will be noted throughout follow-up. It is recommended that bone lesions be followed closely by investigators with comments and measurements whenever possible for retrospective review.

Non-measurable disease

Non-measurable disease is all other lesions (or sites of disease), including small lesions (longest diameter < 20 mm with conventional techniques or < 10 mm using spiral CT scan). Leptomeningeal disease, ascites, pleural or pericardial effusion, inflammatory breast disease, lymphangitic involvement of skin or lung, abdominal masses/abdominal organomegaly identified by physical exam that is not measurable by reproducible imaging techniques are all non-measurable.

